1.2.2 Clinical Background

The experience with GDC-8264 in humans consists of one Phase I study in healthy subjects (GP41678) and one Phase 1 study in subjects with kidney failure requiring dialysis and matched healthy controls (GP42995).

Study GP41678 is a first-in-human, single-center, randomized, double-blinded, placebo-controlled study evaluating the safety, tolerability, and pharmacokinetics of oral GDC-8264 in healthy subjects. The single ascending dose (SAD) stage evaluated doses from 5 mg to 225 mg; the multiple ascending dose (MAD) stage evaluated 50 mg once a day (QD) and 100 mg QD for 14 days. The study also explored the effect of food on the pharmacokinetics of GDC-8264 and the CYP3A induction effect of GDC-8264.

GDC-8264 was well tolerated at all dose levels evaluated in Study GP41678. No individual or group stopping criteria were met; there were no deaths, no serious or severe adverse events, and no clinically significant laboratory, ECG, or vital sign findings related to GDC-8264. Treatment-related adverse events were generally of mild severity.

Pharmacokinetic (PK) analyses from the SAD portion of Study GP41678 indicate that GDC-8264 peak concentrations (C_{max}) were observed at 1.29–4.00 hours (median t_{max}) after the administration of GDC-8264 as single doses over the dose range from 5 mg to 225 mg. The geometric mean elimination half-life $(t_{1/2})$ after single-dose administration ranged from 10.4 to 13.3 hours over this dose range, indicating that once-daily dosing is appropriate and that the t1/2 is independent of dose and formulation. Exposure parameters C_{max}, AUC_{0-24 hr}, and AUC from Time 0 to infinity [AUC_{inf}]) for the tablet formulation at single doses of 75 mg, 150 mg, and 225 mg increased proportionally with dose. Inter-individual exposure variability is low to moderate and ranges from 6.70% to 52.9%. Under fed conditions, C_{max} is approximately 21% higher and median t_{max} increases from 3 to 4 hours, compared with fasted administration, but overall exposure (AUC_{0-24 hr} and AUC_{inf}) is comparable under fasted and fed conditions. Hence, GDC-8264 can be given without regard to food. Low renal excretion of unchanged GDC-8264 was observed at all doses (mean % of GDC-8264 dose excreted in urine of 0.16%–0.22%). Geometric mean renal clearance was similar for all doses and ranged from 0.00901 L/h after 5 mg of GDC-8264 to 0.0119 L/h after 75 mg of GDC-8264 (fed).

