Data arising from sample analysis, including data on genomic variants, will be subject to the confidentiality standards described in Section 8.4.

Given the complexity and exploratory nature of exploratory biomarker analyses, data derived from these analyses will generally not be provided to investigators or patients unless required by law. The aggregate results of any conducted research will be available in accordance with the effective Sponsor policy on study data publication.

4.5.10 Electrocardiograms

Single ECG recordings will be obtained at specified timepoints, as outlined in the schedule of activities (see Appendix 1), and may be obtained at unscheduled timepoints as indicated.

Lead placement should be as consistent as possible. ECG recordings must be performed after the patient has been resting in a supine position for at least 10 minutes. All ECGs are to be obtained prior to other procedures scheduled at that same time (e.g., vital sign measurements, blood draws) and should not be obtained within 3 hours after any meal, if possible. Circumstances that may induce changes in heart rate, including environmental distractions (e.g., television, radio, conversation) should be avoided during the pre-ECG resting period and during ECG recording.

For safety monitoring purposes, the investigator must review, sign, and date all ECG tracings. Paper copies of ECG tracings will be kept as part of the patient's permanent study file at the site. Digital recordings will be stored at the site.

If at a particular postdose timepoint the mean QTcF is > 500 ms and > 60 ms longer than the baseline value, another ECG must be recorded, ideally within the next 5 minutes, and ECG monitoring should continue until QTcF has stabilized on two successive ECGs. The MAGIC Principal Investigator and the Medical Monitor should be notified. Standard-of-care treatment may be instituted per the discretion of the investigator. If a PK sample is not scheduled for that timepoint, a PK sample may be obtained, at the discretion of the MAGIC Principal Investigator or the Medical Monitor. A decision on GDC-8264 discontinuation should be made, as described in Section 5.1.2.3. The investigator should also evaluate the patient for potential concurrent risk factors (e.g., electrolyte abnormalities, co-medications known to prolong the QT interval, severe bradycardia).

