Appendix 1 Schedule of Activities

		Treatment Periods									Safety Follow-Up Period			
	Screenª		Mandat on D	ory Tre ays 1–	atment 28 ^b		Optional Treatment Extension ^b			Follow-Up Visit 1 º	Follow-Up Visit 2/ET Visit ^d	UV e	Long-Term Follow-Up ^f	
Day (Window)													NA	
Informed consent h	x													
Demographics	x													
Medical history and baseline conditions	x													
Vital signs ⁱ	x	x		x		x		x		x		X	X	
Weight ^j	x	x	x	x	x	x		x		x		x		
Height	x													
Complete physical examination ^k	x					x				x				
Limited physical examination		x		x								х	x	
Neurologic examination ^m	x	x m	x ^m			x	x m			x		x	x	
Single 12-Lead ECG	x	x				x				x			x	
Hematology ⁿ	x	x	x	x	x	x	x	x	x	x		x	Хo	
Chemistry ^p	x	x	x	x	x	x	x	x	x	x		x	Хo	
Coagulation (INR, aPTT, PT)	x													
Pregnancy test ^q	x					x						X d	x	

GDC-8264—Genentech, Inc. 107/Protocol GA43861, Version 4
		Treatment Periods					Safety F Per	ollow-Up riod						
	Screenª		Mandatory Treatment on Days 1–28 ^b			0	ptional Exter	Treatmonsion ^b	ent	Follow-Up Visit 1 º	Follow-Up Visit 2/ET Visit ^d	UV e	Long-Term Follow-Up ^f	
Day (Window)													NA	
Serum sample (ST2 and REG3 α) for MAP calculation	x	x	x	x	x	x	x	x	x	x		x	X٢	X s
MAGIC aGVHD Staging	x	х	x	x	x	x	x	х	х	x	x	х	x	х
Residual biopsy tissue sample (if available) ^t	xt							X ^t						
GDC-8264 administration [#]		0	nce a da	ay on D	ays 1–:	28	Once	a day o	n Days	29–56				
Clinical response assessment			x	x	x	x	x	x	x	x	x	x	x	x
Chronic GVHD staging ^v	x		x	x	x	x	x	х	x	x	x	x	x	x
Corticosteroid-refractory aGVHD			x	x	x	x	x	x	x	x				
Plasma PK sample *					See	Apper	ndix 2						хw	
Serum samples for exploratory biomarkers ^{w, s}	x		See Appendix 2						x w	Хw	X ^s			
Buccal scraping sample for WGS/WES ^{x, y}		x												
Concomitant medications ^z	x	х	X	x	х	x	x	Х	х	X	x	x	X	X ^z
Adverse events aa	х	x	X	x	x	x	x	x	x	x	x	x	x	X ^{aa}

		Treatme	nt Periods	^o eriods		Safety Follow-Up Period			
	Screen ^a	Mandatory Treatment on Days 1–28 ^b	Option	nal Treatm xtension ^ь	ent	Follow-Up Visit 1 º	Follow-Up Visit 2/ET Visit ^d	UV e	Long-Term Follow-Up ^f
Day (Window)								NA	
Malignancy relapse or progression follow-up ^{bb}							x		x
Survival follow-up bb							х		x

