aGVHD=acute graft-versus-host disease; ET=early termination; MAGIC=Mount Sinai Acute GVHD International Consortium; MAP=MAGIC algorithm probability; NA=not applicable; PK=pharmacokinetic; Screen=screening; UV=unscheduled visit; WES=whole exome sequencing; WGS=whole genome sequencing.

Notes: All assessments should be performed within the designated window for the scheduled visit, unless otherwise specified. On treatment days, all assessments should be performed prior to dosing, unless otherwise specified.

- ^a Results of standard-of-care assessments performed prior to obtaining informed consent and within assessments do not need to be repeated for screening.
- ^b At the investigator's discretion, patients with partial response, very good partial response, or complete response (as defined in Section 3.1.4) on may receive GDC-8264 at the same dose level administered once a day for 28 additional days (Days 29–56). If treatment extension is anticipated, it is recommended that the same visit be scheduled such that there is no interruption in daily GDC-8264 dosing.
- ^c Patients who complete the treatment period will return to the clinic for safety follow-up visit 1 at
- ^d Patients who complete the treatment period will return to the clinic for safety follow-up visit 2 at Patients who discontinue from the study prior to completing the safety follow-up period will return to the clinic for an early termination visit
- e An unscheduled visit is a visit or unscheduled assessment during the treatment or safety follow-up periods (or second of the periods (or second of the periods)) that is not specified by the protocol during which a patient undergoes additional assessments for evaluation of potential adverse event(s). Assessments included in the unscheduled visit should be performed as clinically indicated.

GDC-8264—Genentech, Inc. 109/Protocol GA43861, Version 4

- f Required follow-up information will be collected via telephone calls and/or clinic visits approximately after initiation of GDC-8264 dosing, or until death, loss to follow-up, or study termination by the Sponsor.
- ^g It is recommended that all staging and efficacy measures be captured as close to as possible, including predose biomarker samples (see Appendix 2).
- ^h Informed consent must be documented before any study-specific screening procedure is performed, and may be obtained more than initiation of study treatment.

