- ⁱ Vital signs include respiratory rate, pulse rate, and systolic and diastolic blood pressure, and temperature. During the treatment period, for patients who are hospitalized, vital signs obtained closest to and prior to the dose of GDC-8264 should be reported as the vital signs for the scheduled study visit.
- ^j Patient weight should be obtained on each day when PK samples are drawn. For the steady-state PK visit, weight should be measured once on the initial day of sample collection. See Appendix 2 for the schedule of PK samples.
- ^k A complete physical examination includes evaluation of the head, eyes, ears, nose, and throat, and the cardiovascular, dermatologic, musculoskeletal, respiratory, gastrointestinal, and neurologic systems; genitourinary examinations may be performed if clinically indicated.
- ¹ A limited, symptom-directed examination should be performed at specified timepoints or as clinically indicated.
- The targeted neurologic assessment will be focused on motor abnormalities and may include an assessment of orientation, facial and eye movement assessment (e.g., through evaluation of cranial nerves III–VII, XI, XII), and a check for postural tremor or myoclonic movements in the outstretched arm(s). The same assessment performed at baseline should be repeated at each timepoint. The neurologic examination during the treatment period should be performed postdose. On Day 1, the neurologic examination should be performed approximately 2 (±1) hours after the first dose of GDC-8264.
- ⁿ Hematology includes WBC count, RBC count, hemoglobin, hematocrit, platelet count, and differential count (neutrophils, eosinophils, basophils, monocytes, lymphocytes, other cells).
- If patients are receiving strong inhibitors of CYP3A (such as azole anti-infectives) in combination with GDC-8264, perform safety laboratory tests twice a week during treatment with GDC-8264.
- P Chemistry panel (serum or plasma) includes bicarbonate or total carbon dioxide (if considered standard of care for the region), sodium, potassium, chloride, glucose, BUN or urea, creatinine, total protein, albumin, phosphate, calcium, total and direct bilirubin, ALP, ALT, and AST.

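### No scheduled ECG is tied to the hours near peak concentration, so the QTcF rules can act only on trough, off-drug or unscheduled readings

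*Combined protocol and SAP*

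**What the plan says.** The general note to the Appendix 1 Schedule of Activities sets a default: "On treatment days, all assessments should be performed prior to dosing, unless otherwise specified". One assessment is clearly taken out of that default: "The neurologic examination during the treatment period should be performed postdose", with a target of 2 (±1) hours after the first dose on Day 1. The row labelled "Single 12-Lead ECG" carries no footnote letter.

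Section 4.5.10 sets no times of its own: "Single ECG recordings will be obtained at specified timepoints, as outlined in the schedule of activities (see Appendix 1"). It adds that ECGs "may be obtained at unscheduled timepoints as indicated". It then gives an action rule that begins "If at a particular postdose timepoint the mean QTcF is > 500 ms and > 60 ms longer than the baseline value" and says what to do when no PK sample is scheduled at that time. Table 7 has further QTcF criteria for withholding or stopping study drug, and also asks for a PK sample if none is already due.

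Section 1.2.2 reports median tmax of 1.29 to 4.00 h and geometric mean half-life of 10.4 to 13.3 h over single doses of 5 to 225 mg in healthy subjects.

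**The concern.** The QTcF rules read as though some ECGs are recorded in the hours after a dose and may coincide with PK samples. Appendix 2 does schedule serial post-dose PK sampling on Day 1 and at the steady-state PK visit, but Appendix 1 pairs no post-dose ECG with either. A site that follows the schedule exactly will take every planned on-treatment ECG when concentration is at its lowest.

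The trial exists to choose between 35 mg and 75 mg on safety, PK and efficacy. ECG change is a planned descriptive safety summary (Section 6.4), and the relation of exposure to safety is an exploratory objective. If QTcF did respond to concentration, readings at trough would show the smallest effect and the smallest absolute gap between the doses.

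**Working it through.** The plan states no figure for this point, so there is none to reproduce.

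**Step 1: where the ECGs fall.** Counting screening as the first column, the ECG row is marked in columns 1, 2 (Day 1), 6 and 10, and at the unscheduled visit. Columns 3 to 5 are blank. None of the visible Appendix 1 footnotes (a to bb) gives an ECG time. The day row is redacted, so columns are matched to visits by order and by Appendix 2. There, one visit allows PK at any time for patients ending mandatory treatment and requires it pre-dose for those continuing. Four extension-only visits follow, all pre-dose.

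| ECG mark | Time relative to dose | Drug present |
|---|---|---|
| Screening | before any dose | none |
| Day 1 | before first dose (default) | none |
| 6th column (inferred end of mandatory treatment) | pre-dose if continuing, otherwise after the last dose | trough or falling |
| 10th column (extension patients only) | pre-dose, or after the last dose | trough or falling |
| Unscheduled visit | as indicated | not planned |

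Scheduled ECGs tied to the hours near tmax: 0. Scheduled ECGs after at least one dose: at most 2, or 1 for a patient who does not extend.

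**Step 2: exposure at a pre-dose reading.** With once-daily dosing, a pre-dose ECG falls about 24 h after the previous dose, so 24 − 4.00 = 20.0 h to 24 − 1.29 = 22.7 h after the peak.

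Simple log-linear decline, trough/peak = 0.5^((24 − tmax)/t½):
- low end: 0.5^((24 − 1.29)/10.4) = 0.22
- high end: 0.5^((24 − 4.00)/13.3) = 0.35

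One-compartment oral model at steady state (an assumption), with the absorption rate ka solved to give the stated tmax and k = ln 2/t½. Concentration is proportional to e^(−kt)/(1 − e^(−24k)) − e^(−ka·t)/(1 − e^(−24ka)):
- t½ 10.4 h, tmax 1.29 h: 0.224
- t½ 11.4 h, tmax 3 h: 0.292
- t½ 13.3 h, tmax 4 h: 0.371

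Restricting tmax to the 3 h (fasted) and 4 h (fed) medians gives 0.261 to 0.371.

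**Step 3: is the model reasonable?** The accumulation ratio 1/(1 − 0.5^(24/t½)) is 1.30 at 11.4 h, against 1.31 reported for AUC at 100 mg. It is 1.29 at 11.2 h, against 1.39 reported at 50 mg. For 100 mg QD, Section 3.3.1.1 gives AUC 21,200 and Cmax 1670, so average/peak = 21,200/24/1670 = 0.53. The model at 11.4 h gives 0.57 to 0.65. The observed profile is somewhat more peaked than the model, so the modelled trough/peak ratio is, if anything, on the high side.

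**Step 4: recording type.** The 4.5.10 rule is written for a mean QTcF, but the same section schedules single recordings. The text does not say what is averaged.

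**The case against.** A reader might infer that the 4.5.10 rule has no scheduled reading to act on. The documents do not support that. Appendix 2 describes a sample drawn about 24 h after a dose and before the next one as a 24-hour postdose sample, so a pre-dose ECG later in treatment is post-dose in the plan's own usage. The sustained-QTcF criteria in Table 7 carry no post-dose condition, and unscheduled ECGs are allowed. The rules can operate. What is missing is a planned reading near peak.

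The different timing can also be defended as risk-based. The named potential risks are serious infection and seizure, and post-dose neurologic examination is listed as mitigation for them. QT prolongation is not named. The first-in-human study reported no clinically significant ECG findings related to drug, at single doses up to 225 mg and at 100 mg QD for 14 days, both above the planned doses. The co-primary safety endpoint is adverse events, ECGs are summarized descriptively, and about 20 patients per cohort were not chosen on power. This stands: it lowers the priority and rules out any claim that a real dose difference will be missed. It does not remove the mismatch between an action rule framed around post-dose timepoints and a schedule that defaults to pre-dose. Section 3.3.4 also allows that PK in these patients may differ from healthy subjects.

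The redactions matter too. The default binds only on treatment days, so whether columns 6 and 10 are dosing days decides which ECGs could be re-timed. An ECG time in redacted text cannot be fully excluded.

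**Conclusion.** The point holds in this limited form. On the visible text, no scheduled ECG is tied to the hours near tmax. Day 1 is drug-free, and the two later readings fall at trough, about 22 to 37% of peak, or after the last dose. The QTcF rules in 4.5.10 and Table 7 therefore act only on trough, off-drug or unscheduled readings.

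The percentage rests on healthy-subject PK and a simple model, because the simulated Cmax and Cmin for 35 mg and 75 mg are redacted. The matching of columns to visits is inferred. Nothing in the documents shows a concentration-related QT effect, so this is a gap in detection and an internal mismatch, not evidence of harm.

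**What to change.** Reconcile Section 4.5.10 with Appendix 1 by adding a footnote to the ECG row that gives its time relative to dose. Then re-time one existing ECG to a same-day post-dose reading near tmax, paired with a scheduled PK sample. There are two ways:

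- **Day 1.** Record the ECG post-dose alongside the 2 (±1) h neurologic examination, with the screening ECG as baseline. This reaches every treated patient. From the reported Cmax accumulation ratios of 1.41 and 1.37, a first-dose peak is about 1/1.41 = 71% to 1/1.37 = 73% of the steady-state peak. The cost is the Day 1 pre-dose baseline.
- **Steady-state PK visit.** Shift the 6th-column ECG to this visit, which on the inferred matching has no ECG mark now. This reads at steady-state peak. The cost is the end-of-mandatory-treatment reading.

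A footnote alone cannot make the 6th-column ECG post-dose for patients who do not extend, since they appear to take no dose that day. Keeping all current readings means one short added recording. Either way, some outpatient visits run slightly longer.

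Also state in 4.5.10 whether a mean QTcF applies when single ECGs are taken and, if so, over which recordings. The QTcF thresholds and the actions attached to them are not part of this change.

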Appendix 2 Schedule of Pharmacokinetic and Exploratory Biomarker Samples

		Sample Type			
Visit	Timepoint	GDC-8264 PK (plasma)	Exploratory Biomarker (serum)		
Screening	Any time	_	Biomarker		
	Predose (up to 2 hours before dosing)	GDC-8264 PK	Biomarker		
	after dosing	GDC-8264 PK	_		
	after dosing	GDC-8264 PK	_		
	dosing after	GDC-8264 PK	_		
	after dosing	GDC-8264 PK	_		
	after dosing	GDC-8264 PK	_		
) hours after dosing ^a	GDC-8264 PK	_		
	after Day 1 dosing (and prior to Day 2 dosing) ^a	GDC-8264 PK			
Steady-state PK visit:	Predose (up to 2 hours before dosing)	GDC-8264 PK			
(hospitalized patient) or (outpatient) b	after dosing	GDC-8264 PK	_		
(after dosing	GDC-8264 PK	_		
	after dosing	GDC-8264 PK	_		
	after dosing	GDC-8264 PK	_		
	after dosing	GDC-8264 PK	_		
	hours after dosing ^a	GDC-8264 PK	_		
	after prior day dosing (and prior to dosing on this day) ^a	GDC-8264 PK	—		
b	Predose (up to 2 hours before dosing)	GDC-8264 PK	Biomarker		

		Sample T	уре
Visit	Timepoint	GDC-8264 PK (plasma)	Exploratory Biomarker (serum)
b	Predose (up to 2 hours before dosing)	GDC-8264 PK	Biomarker
b	Predose (up to 2 hours before dosing)	GDC-8264 PK	Biomarker
	Mandatory treatment: any time Optional TE: Predose (up to 2 hours before dosing)	GDC-8264 PK	Biomarker
(Optional TE only)	Predose (up to 2 hours before dosing)	GDC-8264 PK	Biomarker
(Optional TE only)	Predose (up to 2 hours before dosing)	GDC-8264 PK	Biomarker
(Optional TE only)	Predose (up to 2 hours before dosing)	GDC-8264 PK	Biomarker
(Optional TE only)	Predose (up to 2 hours before dosing)	GDC-8264 PK	Biomarker
Unscheduled visit ^{c, d, e}	_	GDC-8264 PK	Biomarker
Follow-up visit 2 ^f			Biomarker
	_	_	Biomarker

Appendix 2: Schedule of Pharmacokinetic and Exploratory Biomarker Samples

aGVHD=acute graft-versus-host disease; PK=pharmacokinetic; QTcF=QT interval corrected through use of Fridericia's formula; TE=treatment extension.

Notes: Please see the laboratory manual for sample details and processing instructions. See Appendix 1 for visit windows.

- ^a The 12-hour and 24-hour postdose samples are optional if patient is not hospitalized. Samples for hospitalized patients should be collected.
- ^c An unscheduled visit is a visit or unscheduled assessment during the treatment or safety follow-up periods (or during which a patient undergoes additional assessments for evaluation of potential adverse event(s).

Appendix 2: Schedule of Pharmacokinetic and Exploratory Biomarker Samples

- ⁴ If a patient is diagnosed with corticosteroid-refractory aGVHD or aGVHD flare, a serum sample for exploratory biomarkers should be obtained on the day of diagnosis. See Section 3.1.4 for key definitions and details on response criteria.
- ^e PK samples should be obtained if prolonged QTcF is observed or if a patient experiences seizure or convulsion (obtain PK sample as soon as possible). If an unscheduled visit occurs after **sector** or after **sector** for patients entering the optional treatment extension, a PK sample should not be obtained.
- ^f Patients who complete the treatment period will return to the clinic for a safety follow-up visit at the clinic for a safety follow-up visit
 ^f Patients who discontinue GDC-8264 prematurely will return to the clinic for a safety follow-up visit

Appendix 3 Ann Arbor Scoring

The Mount Sinai Acute GVHD International Consortium (MAGIC), a group of 25 hematopoietic cellular transplantation centers conducting graft-versus-host disease(GVHD) research, has validated an algorithm that combines two gastrointestinal biomarkers (interleukin [IL]-33 receptor suppressor of tumorigenesis 2 [ST2]) and regenerating islet-derived 3-alpha [REG3 α]) into a single value that estimates the probability of 6-month non-relapse mortality (NRM) for individual patients, known as the MAGIC algorithm probability (MAP). The MAP also predicts response to treatment, maximum aGVHD severity, and overall survival. The MAP is able to separate patients into three distinct risk strata (Ann Arbor scores 1, 2, and 3). The concentration of ST2 and REG3 α are determined by validated ELISA. The MAP is calculated using the following formula:

MAP = 1 - EXP(- EXP(0.577*LOG(REG3α,10)+1.844*LOG(ST2,10) - 11.263))

Ann Arbor aGVHD score cut-offs are as follows:

- Ann Arbor Score 1: MAP < 0.141
- Ann Arbor Score 2: $0.141 \le MAP \le 0.290$
- Ann Arbor Score 3: MAP > 0.290

References

- Hartwell MJ, Özbek U, Holler E, et al. An early biomarker algorithm predicts lethal graftversus-host disease and survival. JCI Insight 2017; 2:e89798.
- Srinagesh HK, Özbek U, Kapoor U, et al. The MAGIC algorithm probability is a validated response biomarker of treatment of acute graft-versus-host disease. Blood Adv 2019;3:4034–42.

